4.2.2 Full Analysis Set (FAS)

Full Analyses Set is defined as all subjects included in the clinical investigation with at least one pupillometric measurement.

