Figure 1. Summary of the different parts of PreVict Drugs to be used in this investigation. The subject will perform self-administered eye measurements through the app using the smartphone camera. The results from the eye measurements will be stored in the database and further analysis will be performed in the external computer whereafter these results will also be stored in the database. Once the investigation is completed, the data results will be transferred to the R&D cloud. The careportal will in this investigation be used only for providing a subject access to the app.

The eye measurements with PreVict Drugs will in this investigation be performed by the participating subjects. The site personnel will assist as required. A measurement is started in the app by the subject where a video of the face area is recorded through the camera of the study specific smartphone. Before the video recording is started, it will be confirmed that the ambient light is acceptable for the intended imaging. If required, the app will guide the subject to a location where the light condition is suitable. During a test with

	Clinical Investigation Code: KC09-108 Clinical Investigation Plan KCclin02	Revision: A
---	---	----------------

Previct Drugs app, three different videos, i.e., measurements, are recorded whereafter the videos are automatically processed. The three different measurements that will be performed during one test are:

- 1) Pupillary light reflex (PLR)
- 2) Non-convergence (NC)
- 3) Horizontal nystagmus (NY)

For the PLR-measurement, the subject will be filmed while the led-lamp on the smartphone is turned on. For the NC-measurement, the subject will be filmed while receiving instructions to cross the eyes. For NY-measurement, the subject will be filmed while looking to the far side.

The three different measurements rely on pupil size (PLR) and iris position (NC and NY). The size and position indicators are extracted using an algorithm implementing artificial intelligence (AI). In parallel with the three pupillometry measurements, the color of the white of the eye is estimated in the PLR measurement (because the led lamp of the mobile phone evens out some of the effects of ambient light) and user motion patterns (tremor) is evaluated in the NY measurement.

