- After a measurement is completed, an analysis will start to verify if the measurement was performed successfully or not. The subject will be notified accordingly in the app. If the measurement is not performed successfully, the subject should try to perform the measurement one more time.
- In total three different measurements, i.e., video recordings (NC, NY and PLR), will be performed after each other. Thereafter the test is completed for the subject.
- The measurements will be automatically processed to the pupillometric variables and thereafter the videos and the pupillometric variables will be transferred to the database. The videos and variables will not be available in the app/smartphone any longer.

[figure not shown]
For further guidance, please see the study specific IFU [13].

The database:

The database will be used in the investigation for storage of the videos, pupillometric variables, and key features during the investigation.

The external computer:

The external computer will be used for processing pre-defined key features from the pupillometric variables.

Direct access to the videos is limited to the data scientists at the sponsor’s software department. Most videos will not be inspected by anyone as they can be processed automatically by the pre-defined mathematical and algorithms model.

The R&D cloud:

Once the investigation is complete, the pupillometric variables, key features, and cut-out eye areas of the videos will be transferred to a separate and secure R&D cloud for storage. The other parts of the videos will be destroyed. The data in the R&D cloud will be used for the continued development of PreVict Drugs after the investigation. Once transferred to R&D cloud, data is permanently deleted from the database. All storage is encrypted and entirely hosted within the European Union/Sweden.

	Clinical Investigation Code: KC09-108 Clinical Investigation Plan KCclin02	Revision: A
---	---	----------------

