4.2 Definition of Analysis Sets

4.2.1 Safety Analysis Set (SAF)

It is stated in the Clinical Investigational Plan (CIP) that all analyses will be performed on the Full Analyses Set (FAS). Full Analyses Set is defined as all subjects included in the clinical investigation with at least one pupillometric measurement. Hence, the SAF and the FAS will be identical.

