4.2.3 Use of Analysis Sets

All analyses will be performed on the Full Analyses Set (FAS).

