7.1.2 Analysis

1. Frequency table for each of the 18 questions with numbers and percentage for each alternative.
2. For answers "very easy" and "easy" and answers, "very good" and "good" favoring Kontigo product will be added together and given with numbers, percentages and 95% confidence intervals.

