7.1.3 Presentation

All data collected from patients included in the FAS will be presented with summary statistics, i.e. number of observations, number of missing observations, minimum value, median value, maximum value and standard deviation for continuous data and frequency and percentage for categorical data. Summary statistics will include number of subjects with data, number of subjects with missing data, mean, standard deviation, median, minimum and maximum for continuous data and frequency and percentage for categorical data.

Table with summary statistics will be divided by treatment group, visit and relevant stratification factors such as the light conditions.

An example in the tables below.

Table 1 Example of a table presenting data for continuous variable.

| Statistica | Group 1 | Group 2 | Group 3 | Group 4 |
|--------------------|---------|---------|---------|---------|
| N | X | X | X | X |
| Missing | X | X | X | X |
| Min | X.XX | X.XX | X.XX | X.XX |
| Median | X.XX | X.XX | X.XX | X.XX |
| Mean | X.XX | X.XX | X.XX | X.XX |
| Standard deviation | X.XX | X.XX | X.XX | X.XX |

Table 2 Example of a table presenting data for a categorical variable.

| Statistica | Group 1 | Group 2 | Group 3 | Group 4 |
|------------|---------|---------|---------|---------|
| Missing | X (%) | X (%) | X (%) | X (%) |
| Category 1 | X (%) | X (%) | X (%) | X (%) |
| Category 2 | X (%) | X (%) | X (%) | X (%) |
| : | : | : | : | : |
| : | : | : | : | : |
| Category n | X (%) | X (%) | X (%) | X (%) |

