7.2.2 Analyses

Secondary 1

For each subject, the proportion of approved measurements over all measurements during visit 1 will be calculated for each of PLR, NC, NY, TR and Redness. The two light conditions will be analyzed separately for for PLR. The follow-up analyses will be analyzed separately and compared with the success rate at visit 1.

Secondary 2

For each subject, the proportion of approved refined measurements over all measurements during visit 1 will be calculated for each of PLR, NC, NY, TR and Redness.. The distribution over subjects in each drug class will be given with Mean, SD, median, minimum and maximum. The two light conditions will be analyzed separately. The follow-up analyses will be analyzed separately. and compared with the success rate at visit 1.

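### The primary usability analysis and the safety summaries leave out an observed subject who never obtains a video, which is a clear usability failure; the effect is probably small or nil

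*SAP*

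**What the plan says.** SAP 4.2.2 defines the analysis set: "Full Analyses Set is defined as all subjects included in the clinical investigation with at least one pupillometric measurement". Protocol 12.1 and the synopsis use the same definition, and none of these places ties the measurement to a particular visit. SAP 4.2.3 applies the set throughout, SAP 7.1.3 repeats this for the primary endpoint ("All data collected from patients included in the FAS will be presented with summary statistics"), and SAP 4.2.1 carries it over to safety: "Hence, the SAF and the FAS will be identical".

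The primary endpoint (protocol 10.2, SAP 7.1.1) is a set of 18 questions answered by site staff who watch the subject use the app. SAP 7.1.2 asks for a frequency table per question. It then pools the two best answers on the easy and good scales, which are "favoring Kontigo product will be added together and given with numbers, percentages and 95% confidence intervals".

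On what counts as a measurement, protocol section 6 says that during a test "three different videos, i.e., measurements, are recorded whereafter the videos are automatically processed". Protocol 6.9 uses the word in the same way: "In total three different measurements, i.e., video recordings (NC, NY and PLR), will be performed after each other". SAP 7.2.2 keeps measurements apart from approved measurements: "the proportion of approved measurements over all measurements during visit 1 will be calculated for each of PLR, NC, NY, TR and Redness".

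**The concern.** The primary objective is to learn whether the interface suits patients with substance use disorder. Entry to the primary analysis requires a recording, which the subject gets only by using that interface. Someone who tries under observation and never produces a recording is among the plainest usability failures the study could see, and the rule removes that person.

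The documents foresee the situation. The app checks light and surroundings before it records (protocol 6 and 6.9). SAP 6.4 provides for a test that cannot be conducted. Question 16 asks whether the subject managed the test after support. Protocol 10.8.6 says it is unknown how well subjects can perform a measurement and treats this as an important usability question.

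At stake is a description of usability that is slightly too favourable. Because the safety set equals the same set, the subject is also missing from the safety summaries in SAP 7.3.2.

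**Working it through.** **Who is lost.** The documents use *measurement* for a recorded video, and SAP 7.2.2 has approved measurements in the numerator and all measurements in the denominator. A video that fails quality control is therefore still a measurement. Subjects who struggle, need help or fail quality control remain in the set. The only eligible, observed subject who leaves is one with no video at any visit.

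**What the subject is lost from.** All 18 frequency tables, including questions 14 to 18 (support needed, ability after support, number of efforts, likely success at home), which can be answered without a recording. Also the pooled percentages. The response options are not in the documents. By wording, questions 14 to 18 do not look like easy or good items, so the pooled percentages more plausibly concern items such as 1, 2, 4, 6, 8, 10 and 12.

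**Size.** The plan states no figure to reproduce. Inputs:
- n = 30, the enrolment aim (protocol 12.2, SAP 4.1), and n = 15, the lower end in protocol 10.6.4.
- One subject dropped who would be rated unfavourably on the item (assumed).
- x favourable ratings among the others (assumed).
- Exact Clopper-Pearson 95% intervals (assumed; the SAP names no method).

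Shift = x/(n−1) − x/n = x/[n(n−1)]. It is largest when everyone else is rated favourably (x = n−1), where it equals 1/n: 1/30 = 3.3 points and 1/15 = 6.7 points.

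| n | Current set | All observed | Shift |
|---|---|---|---|
| 30 | 23/29 = 79.3% (60.3–92.0) | 23/30 = 76.7% (57.7–90.1) | 23/870 = +2.6 points |
| 30 | 29/29 = 100% (88.1–100) | 29/30 = 96.7% (82.8–99.9) | 29/870 = +3.3 points |
| 15 | 11/14 = 78.6% (49.2–95.3) | 11/15 = 73.3% (44.9–92.2) | 11/210 = +5.2 points |
| 15 | 14/14 = 100% (76.8–100) | 14/15 = 93.3% (68.1–99.8) | 14/210 = +6.7 points |

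In the first and third rows the intervals are about 32 and 46 to 47 points wide. With nobody dropped the shift is zero.

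The direction is not fixed for every item. If the dropped subject would be rated favourably, as is possible for question 1 on handling the phone, the current set gives 22/29 = 75.9% against 23/30 = 76.7%, a fall of 0.8 points.

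**How often.** This cannot be calculated. The documents give no chance that a test yields no recording. They also disagree on the number of tests: protocol 10.8.1.2 and SAP 6.3 describe one series of four at visit 1, while protocol 10.5 describes two sets of four at each visit. Those passages must be reconciled. Any expected count would rest on an invented failure rate and on one of the two readings.

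**The case against.** The strongest reply is that the excluded subject may never exist. A single video from any test at any visit is enough to enter the set. Staff demonstrate the app and assist, the app guides the subject to suitable surroundings, and a failed measurement is repeated (protocol 6.9, SAP 6.4). The post-recording failures described in protocol section 6, poor quality or videos that cannot be processed, leave the subject in. All of this stands, and is why no expected number is given here.

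Second, the loss would be visible. Disposition is summarised (SAP 5.1), performed and successful tests are in the eCRF (SAP 6.4), and patients outside the set are listed (SAP 9). With at most 30 subjects a reader could put one back into the denominator. That is true, but the reported percentages and intervals would still be computed without the subject.

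Third, it is unclear what the observer form would hold for questions 6, 8 and 10 if a test never ran. A blank would count as missing and would not be imputed (SAP 4.7). This stands, and it means that widening the set is not enough without a rule for such a test.

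A reader might infer more than the documents support:
- That all poor performers are screened out. The use of *measurement* as any recorded video contradicts this.
- That the usability result is materially biased. One subject moves it by a small part of the interval width.
- That adverse events would go unseen. All adverse events are recorded (protocol 10.8.4 and 19.2) and listed (SAP 9), and serious events are reported whatever their cause (protocol 19.5).

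**Conclusion.** The point holds and is minor. Entry to the primary usability analysis depends on partial success with the product being rated, and no other analysis set or sensitivity analysis restores a subject with no video. If one such subject is dropped and would be rated unfavourably on a pooled item, the percentage is too high by at most 3.3 points at n = 30 or 6.7 points at n = 15. If none is dropped, nothing changes. The single dropped subject, the unfavourable rating and the interval method are assumptions; the number of such subjects is unknown.

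The study is descriptive with no pass or fail criterion (protocol 12.4 and 12.5), so the harm is a possibly overstated description and not a wrong decision. The safety part is secondary: the subject is missing from the summaries, but the events are still recorded and listed.

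**What to change.** In protocol 12.1 and SAP 4.2, with the synopsis brought into line:

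- Base the primary usability analysis and the safety summaries on all eligible subjects given the phone for the first test at visit 1, whether or not a video resulted. Screening failures stay out. Adverse events in other consented subjects can be listed separately.
- Count a test that could not be performed as not favourable on the item rating that test (question 6, 8 or 10).
- Keep the current set for the secondary pupillometric endpoints, and state that a measurement means any recorded video, approved or not.

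The cost is a few sentences, and possibly a could-not-perform answer on the observer form. The downside for the sponsor is that the reported percentages may be slightly less favourable.

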4.2.3 Use of Analysis Sets

All analyses will be performed on the Full Analyses Set (FAS).

4.3 Definition of Baseline

The baseline is defined as the first visit when the first test with Previct Drugs will be performed.

4.4 Summary Statistics

In general, all data collected will be presented with summary statistics and given in subject data listings (an overview of subject data listings are given in Section 9). Summary statistics will include number of subjects with data, number of subjects with missing data, mean, standard deviation, median, minimum and maximum for continuous data and frequency and percentage for categorical data.

4.5 Significance Level

Only descriptive statistics will be used and hence no p-values is planned to be presented. However, if p-values will be calculated these will be two-sided and p-values less than 5% considered statistically significant. If confidence intervals are constructed these will be 95% and two-sided.

4.6 Multiple Comparisons/Multiplicity

No adjustment for multiplicity of testing can be done as there are no tests.

4.7 Handling of Drop-outs, Missing Data and Outliers

Available data from prematurely withdrawn subjects will be included in the analysis as far as possible. Missing data will not be imputed.

4.8 Adjustment for Covariates

No adjustment for covariates is planned.

4.9 Multicenter Studies

This is a single center study.

4.10 Examination of Subgroups

No examination of subgroups is planned. However, the two light conditions will also be analyzed separately and may be considered as sub-groups analyses.

4.11 Blind Review

Not applicable as this is an uncontrolled study.

5 SUBJECTS

5.1 Subject Disposition

The number of subjects that entered the study, withdrawn subjects, completed subjects and the number of subjects at each visit will be summarized.

5.2 Baseline Characteristics and Demographics

Demographics (e.g., age, gender,) and baseline characteristics (e.g., ECG, relevant medical and surgical history, relevant concomitant medication, timeline follow-back drugs and medicine last 24-hours) will be presented using descriptive statistics.

6 TREATMENT INFORMATION AND EXTENT OF EXPOSURE

6.1 Active Treatment

There is no active treatment involved, the device usability will be tested.

6.2 Placebo Treatment

Not applicable

6.3 Extent of Exposure

At Visit 1, the subject will perform an eye measurement series which consists of four performed measurements:

- 1 Cross-eyes test
- 1 Nystagmus test
- 2 Contraction tests

The contraction tests must be performed under two different light conditions. The subject must begin by performing a cross-eye-test, followed by a nystagmus test, and then a contraction test. Adjust the lighting conditions, wait 1 minute, and then perform the second contraction test.

Additional measurements with PreVict Drugs during follow-up visits are optional for the study subjects. Up to four (4) follow-up visits within one month after completed Visit 1 is allowed.

6.4 Compliance of Investigational Medical Device (IMD)

During each measurement the PreVict Drugs app will inform if the conducted test was approved. If not approved, the subject will be asked to re-do the measurement. If the test cannot be conducted, the subject continues to the next test, or completes the test set, as applicable.

Performed and successful tests are documented in the eCRF for Visit 1 and if applicable for the follow-up visits. The number of attempts per test is not documented in the eCRF. During the on-site visits, compliance is overseen by site personnel. Sponsor is the only part receiving the PreVict Drugs data output. Non-compliance related to PreVict drugs measurements will be documented by the Sponsor, and where applicable be reported as Protocol Deviations.

6.5 Concomitant Medications

Subjects are allowed to continue their regular medication during the clinical investigation. Relevant concomitant medication data will be listed only.

7 STATISTICAL METHODOLOGY

All efficacy parameters will be presented by treatment and visit using summary statistics.

7.1 Primary efficacy endpoint

7.1.1 Definition

The analysis of the following 18 usability questions from the observation of a study subject during a test with PreVict Drugs.

1. Please evaluate the study subject's ability to use the mobile phone?
2. How did you perceive the study subject's ability to follow the instructions given by Previct Drugs?
3. If you experienced that the study subject had difficulties, please select the suitable choice/choices below.
4. How did the study subject experience to put him/herself in the right position to be able to start a test?
5. If you experienced that the study subject had any difficulty, please select the suitable choice/choices below.
6. How would you evaluate the study subject's ability to perform a Cross-eyes test?
7. If you experienced that the study subject had difficulties, please describe:
8. How would you evaluate the study subject's ability to perform a Nystagmus test?
9. If you experienced that the study subject had difficulties, please describe:
10. How would you evaluate the study subject's ability to perform a Contraction Test?
11. If you experienced that the study subject had difficulties, please describe:
12. How did the study subject experience keeping the phone still during the test?
13. If the study subject had difficulties, please select the suitable choice/choices below.
14. In addition to the basic instructions, did the study subject need additional support performing tests with Previct Drugs?

If No, please forward to question no. 17.

15. What type of additional support did the study subject need? Please select the suitable choice/choices below.
16. Was the study subject able to perform the test after receiving additional support?
17. How many efforts did it take the study subject to perform test with Previct Drugs?
18. How likely do you think it is that the study subject will be able to perform tests with Previct Drugs without assistance in a home environment?

7.1.2 Analysis

1. Frequency table for each of the 18 questions with numbers and percentage for each alternative.
2. For answers "very easy" and "easy" and answers, "very good" and "good" favoring Kontigo product will be added together and given with numbers, percentages and 95% confidence intervals.

7.1.3 Presentation

All data collected from patients included in the FAS will be presented with summary statistics, i.e. number of observations, number of missing observations, minimum value, median value, maximum value and standard deviation for continuous data and frequency and percentage for categorical data. Summary statistics will include number of subjects with data, number of subjects with missing data, mean, standard deviation, median, minimum and maximum for continuous data and frequency and percentage for categorical data.

Table with summary statistics will be divided by treatment group, visit and relevant stratification factors such as the light conditions.

An example in the tables below.

Table 1 Example of a table presenting data for continuous variable.

| Statistica | Group 1 | Group 2 | Group 3 | Group 4 |
|--------------------|---------|---------|---------|---------|
| N | X | X | X | X |
| Missing | X | X | X | X |
| Min | X.XX | X.XX | X.XX | X.XX |
| Median | X.XX | X.XX | X.XX | X.XX |
| Mean | X.XX | X.XX | X.XX | X.XX |
| Standard deviation | X.XX | X.XX | X.XX | X.XX |

Table 2 Example of a table presenting data for a categorical variable.

| Statistica | Group 1 | Group 2 | Group 3 | Group 4 |
|------------|---------|---------|---------|---------|
| Missing | X (%) | X (%) | X (%) | X (%) |
| Category 1 | X (%) | X (%) | X (%) | X (%) |
| Category 2 | X (%) | X (%) | X (%) | X (%) |
| : | : | : | : | : |
| : | : | : | : | : |
| Category n | X (%) | X (%) | X (%) | X (%) |

